4.5. ADJUSTED ANALYSIS

Factors for adjustment will be determined as stated above. If there are substantial baseline differences in recent testing across arms, we will adjust for baseline differences using cluster-level

summaries of baseline values. To adjust for other imbalances across arms, we will use endline measurements of these factors for adjustment, and will assume that there will be no substantial changes in these in the months between the baseline and endline surveys. The adjusted analysis will be the primary analysis.

The following covariates will be assessed as potential adjustors:

- Age
- Sex
- Marital status
- Educational attainment
- Assets index (in tertiles)

Logistic regression will be used to adjust for confounding bias at the individual level, adopting a two-stage approach as outlined in Hayes and Moulton (2009). In the adjusted analysis, the regression model will include terms for the individual-level adjustment factors, but not study arm. The fitted model will be used to obtain the difference and ratio of observed and expected events for each cluster. The ratio will be log-transformed as appropriate. A t-test will be used to estimate the risk difference and risk ratio and their respective 95% CIs and p-values. If adjustment for cluster level factors is considered necessary, this will be conducted at the second stage using linear regression, with appropriate adjustment for the degrees of freedom.

Because restricted randomization was used to allocate clinics, we will also report p-value and 95% confidence interval from a permutation test incorporating the restriction parameters described above (Li et al., 2016).

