2.2 Study population and informed consent

Selection of clinics and evaluation areas. The population included in the impact evaluation are all residents ages 16 and older living in selected evaluation villages and areas located in 4 districts.

22 clinics were selected from rural areas within these districts for inclusion in the study. We identified clinics in areas where PSI had existing CBDAs of reproductive health services and that offered ART initiation. 23 clinics met these criteria, and the clinic with the lowest HIV prevalence was removed.

While HIVST distribution will occur across the entire catchment area of randomly selected clinics, evaluation data collection, including both household survey data collection and clinic data extraction, will be conducted only within selected areas. Evaluation villages represent villages selected for inclusion in the household survey. Evaluation areas represent the area of residence for clients whose data will be captured at the clinic.

Two villages in each cluster served as evaluation villages, with one village randomly receiving the baseline survey and the other receiving the endline survey. Eligibility requirement for the evaluation villages include:

- Location within the catchment area of an eligible ART clinic, with the clinic acting as the most dominant source of ARTs for the village.
- Presence of at least one active PSI CBDA.
- Population of at least 250 residents (ages 16 years and older) per village.
- Road access for most/all of the year.
- Sufficient distance and separation from administrative boundaries and other intended evaluation villages to minimise 1) 'contamination' between HIVST and control villages, and 2) missed linkage to events from seeking HIV care at a remote clinic not included in the evaluation.
- Villages delineated by natural boundaries (e.g., rivers, roads, forests, etc.) will be preferentially selected.

Selection of respondents for baseline and endline surveys. Within evaluation villages, all households were enumerated and a variable fraction were selected to ensure that at least 250 residents (16 years and older) within households were surveyed. Within selected households, all eligible household members were interviewed with the basic questionnaire, and 20% of surveyed individuals received an extended questionnaire. All residents (ages 16 years and older) living in households within the intervention area are eligible to receive HIVST from CBDAs.

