4.3. BASELINE COMPARABILITY OF ARMS (STAGE 1 RANDOMIZATION - HIVST INTERVENTION)

Following baseline data collection, we will summarize baseline data by arm by the following characteristics:

- Age
- Sex
- Marital status
- Educational attainment and socioeconomic status measured using assets variables.
- HIV status, previous HIV testing and self-reported ART use

Baseline analyses will be completed before the endline data collection period begins. The study team will identify substantial differences between arms in terms of the above factors (excluding HIV status and self-reported ART use) and adjust for endline measures of these baseline differences in the outcome analysis (see below). This assessment will not be completed using statistical tests, and p-values will not be shown, as any difference will be due to chance if the randomisation was correctly performed.

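### Individual-level adjusters for the primary analysis are chosen from imbalance in the baseline villages, which are only an indirect guide to balance in the different villages surveyed at endline

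*SAP*

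**What the plan says.** The rule has to be assembled from four places in the SAP.

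- **Section 2.2, Study population and informed consent:** each cluster has two evaluation villages, "with one village randomly receiving the baseline survey and the other receiving the endline survey".
- **Section 3.1:** numerators and denominators for the primary outcome come from the endline survey.
- **Section 4.3:** the study team will "identify substantial differences between arms in terms of the above factors". No statistical test is used and no numerical threshold is given. On timing: "Baseline analyses will be completed before the endline data collection period begins".
- **Section 4.5:** "Factors for adjustment will be determined as stated above", which points back to section 4.3. For factors other than recent testing, "we will use endline measurements of these factors for adjustment", and the analysts "will assume that there will be no substantial changes in these in the months between the baseline and endline surveys". Age, sex, marital status, educational attainment and asset tertile are listed only as candidates. The adjusted analysis is primary. Baseline recent testing is handled differently: if it is imbalanced, it enters as a cluster-level summary.

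**The concern.** The covariates of the primary model are selected in villages that contribute no outcome data. The stated justification would serve if the same villages were surveyed twice, because then only change over time could break the link. It says nothing about the change of village. A factor may look balanced across the 11 baseline villages per arm and be unbalanced across the 11 endline villages per arm, in which case the primary model leaves it out. The reverse can also happen. Nothing in the SAP fixes the covariates in advance or covers this case.

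At stake are precision, adjustment for the imbalance actually present in the analysed data, and a primary model that a second analyst could reproduce from the text. At present the model turns on what the team regards as substantial.

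**Working it through.** The SAP gives no figure on this point to reproduce. The reading of the sections establishes the gap; the arithmetic only sizes it.

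**Inputs from the SAP.** 11 clusters per arm (section 2.2, Trial arms); at least 250 residents surveyed per village (section 2.2, Study population); a 30% relative difference on a standard-of-care proportion of 25% to 40% (section 3.1), that is 0.30 × 25 = 7.5 points to 0.30 × 40 = 12 points.

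**Assumptions (not in the SAP).** A binary covariate with prevalence 50%; between-village SD of 0 to 12 points; a covariate–outcome difference of 10 to 20 points.

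**Step 1: how large are chance gaps at endline?** The standard error of the arm difference in covariate prevalence is √(0.25/250 + SD²) × √(2/11). A gap in the outer 20% exceeds 1.28 standard errors.

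| Between-village SD | SE of arm gap | Outer-20% gap | Chance of gap > 5 points |
|---|---|---|---|
| 0 points | 1.35 | 1.7 | under 0.1% (5/1.35 = 3.7 SE) |
| 4 points | 2.17 | 2.8 | 2% (2.3 SE) |
| 8 points | 3.67 | 4.7 | 17% (1.36 SE) |
| 12 points | 5.29 | 6.8 | 35% (0.94 SE) |

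**Step 2: how often would the baseline villages miss such a gap?** Take both arm differences as bivariate normal and flag the outer 20%. If they correlate 0.2, 0.4 or 0.6 (assumed), the baseline survey fails to flag 78%, 72% or 61% of equally extreme endline gaps. These shares are conditional on a gap being present. Per covariate, the chance that a gap arises and is missed is 0.20 × 0.61 to 0.20 × 0.78, or 12% to 16%.

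A simulation with a fixed 5-point threshold, SD 8 or 12 points and prevalence 30% or 50% gives these missed shares:

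| Correlation of true village means | Share of endline gaps > 5 points not flagged |
|---|---|
| 0 | 65–83% |
| 0.5 | 58–73% |
| 0.9 | 33–48% |
| 1.0 | 21–38% |

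The last row is sampling error alone, so the part due to the change of village is the excess over it.

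**Step 3: what does a missed gap do to the risk difference?** Shift = gap × covariate–outcome difference.

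- SD 0 to 4: 1.7 × 0.10 = 0.2 points, to 2.8 × 0.20 = 0.6 points.
- SD 8 to 12: 4.7 × 0.10 = 0.5 points, to 6.8 × 0.20 = 1.4 points.
- A 10-point gap with a 20-point effect: 10 × 0.20 = 2.0 points. This gap is 10/2.17 = 4.6 SE at SD 4 and 10/5.29 = 1.9 SE at SD 12, so it is plausible only if villages differ widely.

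The upper end is 2.0/7.5 = 27% of the smallest planned difference; most combinations are far below that.

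**Step 4: what does a fixed covariate set cost?** The first stage is fitted to about 22 × 250 = 5,500 individuals. Its covariates are individual-level, so the second-stage t-test keeps 22 − 2 = 20 degrees of freedom.

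**The case against.** Much of the case for the plan stands.

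- **This is not bias.** A reader might infer that the rule biases the primary estimate. The documents do not support that. Section 4.3 itself notes that arm differences are due to chance if randomisation was done correctly, and a chance imbalance leaves the estimator right on average. Between-cluster variation from covariate mix is already in the error term of the t-test, and section 4.5 adds a permutation test.
- **The baseline villages are informative.** A reader might also infer that they say nothing about the endline villages. They share a clinic catchment, and which village is surveyed when is random, so the two are exchangeable within a cluster.
- **The judgement is constrained.** Selection is finished before endline collection starts, so outcomes cannot drive it. The candidates are five named factors, and section 4.4 specifies an unadjusted analysis alongside.
- **Mandatory adjustment is not unconditionally safe.** The covariates are measured at least 12 months after distribution began. Adjusting for them is sound only if the intervention affects neither the covariates nor who responds.

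What does not answer the point: a list fixed now protects against outcome-driven selection equally well, without the undefined threshold. The SAP has already chosen to adjust for chance differences in its primary analysis, so the rule should address the sample analysed. The restricted randomisation balances geography, testers, positivity and catchment population, not these five factors.

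**Conclusion.** The point holds as one of prespecification and precision. The covariates of the primary model depend on an unquantified judgement about villages that supply no outcome data, and the stated assumption covers time but not the change of village. The effect is usually modest: roughly 0.2 to 2 points on the risk difference, against a planned 7.5 to 12 points. That range rests on assumed between-village SDs, covariate gaps and covariate effects, none of which the SAP gives.

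The tempting reading that most endline imbalances would be missed should not be taken as a finding. The high miss rates depend on an assumed correlation, apply only when a gap exists, and at small between-village SDs concern gaps of only 2 to 3 points. The change is still worth making, because it is nearly free and removes an ambiguity from the primary analysis.

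**What to change.** 1. In section 4.5, specify the first-stage logistic model with age, sex, marital status, educational attainment and asset tertile, all measured at endline, whatever the baseline imbalance. Remove the imbalance trigger for these individual-level factors in sections 4.3 and 4.5.
2. Replace the assumption of little change over time with the one actually needed: that the intervention does not materially affect these covariates. Marital status is the least certain, so add a sensitivity analysis without it.
3. State separately, before endline data are seen, whether the cluster-level baseline proportion recently tested enters the second stage. It costs one degree of freedom (20 to 19). Removing the trigger without this statement would drop that adjustment by implication.
4. Keep the baseline table as a description of the arms.

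The cost is SAP wording and slight extra analysis. No new data are needed, since section 4.5 already plans to use endline values of any of the five factors. The downside is a small dependence on covariates measured after the intervention began, which the SAP already accepts.

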4.6. METHODS FOR ADDRESSING MISSING DATA

Missing data will be examined for each variable and for each cluster or participant. A systematic assessment of missingness will be conducted to ascertain the reason and possible mechanism for missing data by identifying the quantity of missing data and patterns within the data. Missingness will be particularly examined by cluster and between study arms to assess for systematic biases. Sensitivity analysis for the primary outcome of recent HIV testing will be carried out – comparing complete case analysis results with those where missing outcome status are re-classified as yes and no. Multiple imputation will be considered in the analysis as appropriate.

4.7. PLANNED SUBGROUP ANALYSES

In addition to the main analyses, we will conduct analyses to assess differences in the effect of the HIVST intervention on the primary outcome by sex and age (adolescents ages 16-19 years versus adults ages 20 years and older). We will also estimate the differential impact of the HIVST intervention by socioeconomic status using the assets index.

For the HIVST intervention, analyses of effect modification will be conducted using the method for testing for interaction in community randomized trials developed by Cheung et al. (2008). This method estimates the difference between intervention and control outcomes within each subgroup, then tests the hypothesis that the subgroups have the same intervention effect using a two-sample t-test.

5. PROCESS EVALUATION

Together with the main trial analysis, we will provide quantitative process data summarizing the strength and reach of the intervention, as well as a summary of harms reported in the household survey tabulated by respondent gender and allocation.

A full process evaluation, including both quantitative and qualitative data analysis, will be published separately.

6. OTHER ANALYSES

6.1. ECONOMIC ANALYSES

Economic analyses, including discrete choice analysis and cost-effectiveness analyses, are described separately.

